6.4.2 Safety Procedures

The procedures to monitor safety will be:

- i. Identification and prevalence of adverse events;
- ii. Measurement of Snellen / LogMAR visual acuity at distance;
- iii. [REDACTED]
- iv. Identification and prevalence of device deficiencies and quality complaints.

[REDACTED]

[REDACTED]

- i. [REDACTED]

- [REDACTED]
- [REDACTED]
- [REDACTED]
- [REDACTED]

6.4.4 Study Management Procedures

The procedures to ensure that the study protocol is followed will be;

- i. [REDACTED]
- ii. Study contact lenses fitting as per manufacturer guidelines;

6.5 Study Visit routine

The routine below will be followed: The detailed study routine will be as follow:

Visit 1 – Screening, Enrolment and First Study Contact Lens Dispensing Visit

The routine below will be followed:

- Explanation of the study¹
- Signing of the consent form
- Participant demographics and ocular history questionnaire
- [REDACTED]
- [REDACTED]
- [REDACTED]
- [REDACTED]
- Standard high contrast Snellen visual acuity at distance and near with sphero-cylindrical and best sphere corrections (monocular & binocular)
- [REDACTED] [REDACTED]
- Review of inclusion and exclusion criteria
- Decision to continue with determination of eligibility
- [REDACTED]
- [REDACTED]
- ORDER 1 STUDY INITIAL CONTACT LENS INSERTION AND WEAR FOR 10 MINUTES^{3,4}
- [REDACTED]
- [REDACTED]
- Study contact lens prescription suitability evaluation & decision to dispense or change contact lens power⁵
- Standard high contrast Snellen visual acuity at distance and near with and without best sphere over refraction (monocular & binocular)
- ORDER 1 REMOVE INITIAL CONTACT LENS & INSERT ORDER 1 SECOND CONTACT LENS AND WEAR FOR 10 MINUTES⁶
- [REDACTED]

- [REDACTED]
- [REDACTED]
- [REDACTED]
- [REDACTED]
- [REDACTED]
- [REDACTED]
- [REDACTED]

- [REDACTED]
- Study contact lens prescription suitability evaluation & decision to dispense or change contact lens power⁷
- Standard high contrast Snellen visual acuity at distance and near with and without best sphere over refraction (monocular & binocular)
- ORDER 1 REMOVE SECOND CONTACT LENS & INSERT ORDER 1 THIRD CONTACT LENS AND WEAR FOR 10 MINUTES⁸
- [REDACTED]
- [REDACTED]
- Study contact lens prescription suitability evaluation & decision to dispense or discharge
- Standard high contrast Snellen visual acuity at distance and near with and without best sphere over refraction (monocular & binocular)
- [REDACTED]
- [REDACTED]
- Study product dispensing
- Scheduling

Visit 2 – First Study Contact Lens Follow-up Visit and Second Study Contact Lens Dispensing Visit (7 +/-0 days after Visit 1)

The routine below will be followed:

- [REDACTED]
- [REDACTED]
- [REDACTED]
- [REDACTED]
- [REDACTED]
- Standard high contrast Snellen visual at distance and near without over refraction (monocular & binocular)
- Detailed timed logMAR visual acuity without over refraction (monocular & binocular)
- [REDACTED]
- ORDER 1 CONTACT LENS REMOVAL
- [REDACTED]
- Standard high contrast Snellen visual at distance and near with spherocylindrical correction (monocular & binocular)
- ORDER 2 STUDY INITIAL CONTACT LENS INSERTION AND WEAR FOR 10 MINUTES^{10,11}
- [REDACTED]
- [REDACTED]
- Study contact lens prescription suitability evaluation & decision to dispense or change contact lens power¹²
- Standard high contrast Snellen visual acuity at distance and near with and without best sphere over refraction (monocular & binocular)

- 7 [REDACTED]
- [REDACTED]
- [REDACTED]
- [REDACTED]
- [REDACTED]
- [REDACTED]

- ORDER 2 REMOVE INITIAL CONTACT LENS & INSERT ORDER 2 SECOND CONTACT LENS AND WEAR FOR 10 MINUTES¹³
- [REDACTED]
- [REDACTED]
- Study contact lens prescription suitability evaluation & decision to dispense or change contact lens power¹⁴
- Standard high contrast Snellen visual acuity at distance and near with and without best sphere over refraction (monocular & binocular)
- ORDER 2 REMOVE SECOND CONTACT LENS & INSERT ORDER 2 THIRD CONTACT LENS AND WEAR FOR 10 MINUTES¹⁵
- [REDACTED]
- [REDACTED]
- Study contact lens prescription suitability evaluation & decision to dispense or discharge if third contact lens not suitable
- Standard high contrast Snellen visual acuity at distance and habitual near position with and without best sphere over refraction (monocular & binocular)
- [REDACTED]
- [REDACTED]
- [REDACTED]
- [REDACTED]

Visit 3 – Second Study Contact Lens Follow-up Visit (7 +2/-0 days after Visit 2)

The routine below will be followed:

- [REDACTED]
- [REDACTED]
- [REDACTED]
- [REDACTED]
- [REDACTED]
- Standard high contrast Snellen visual at distance and near without over refraction (monocular & binocular)
- Detailed timed logMAR visual acuity distance and near without over refraction (monocular & binocular)
- Lens mechanical performance evaluation (subjective rating only)
- ORDER 2 CONTACT LENS REMOVAL
- [REDACTED] [REDACTED]
- Standard high contrast Snellen visual at distance and near with spherocylindrical correction (monocular & binocular)
- Overall, [REDACTED] specific contact lens preference questionnaire
- Discharge

¹³ [REDACTED]

- [REDACTED]
- [REDACTED]
- [REDACTED]

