Planned Start Date	15 th August 2022
Overall Study Duration	Six months
Objective(s)	The objectives of the study will be to: 
 i. Compare overall vision satisfaction achieved after one week of wear with Biofinity® Multifocal contact lenses fitted in two different manners [REDACTED]

	[REDACTED]	
	[REDACTED]	
Experimental Design	 Retrospective  Prospective	 Non-Randomized  Randomized (order of testing)
	 Single masked (participant)  Single masked (investigator)  Double masked*  Sponsor masked  Open label * Sub-investigators collecting primary and secondary endpoint data and participants will be masked.	 Single group  Parallel group  Crossover  Contralateral
Control Product	Biofinity® multifocal CE marked silicone hydrogel contact lenses manufactured from comfilcon A by CooperVision Inc. design +1.50D (control contact lens)	
Test Products	Biofinity® multifocal multifocal CE marked silicone hydrogel contact lenses manufactured from stenfilcon A by CooperVision Inc designs +1.50D and +1.50N (test contact lens)	
Study Products Use	The study contact lenses will be used as per their CE marking. The contact lenses will be worn on a daily wear basis removed every night, stored overnight in OPTI-FREE® PureMoist® CE marked storage solution and re-inserted the following morning.	
Study Visits	Three study visits over a two-week period: 
 • Visit 1: Screening/Enrolment/Fitting and First Lens Dispensing • Visit 2 (7 +2/-0 days from Visit 1): First Lens follow up visit, Second Lens Dispensing • Visit 3 (7 +2/-0 days from Visit 2): Second lens follow up visit/Exit 	
	[REDACTED]	
Regulatory Status	This trial requires Ethics Committee (EC) approval prior to initiation.	
Responsibilities	Sponsor	Name: CooperVision International Limited. Contact: [name] [name]
	CRO and Data Management	OCULAR TECHNOLOGY GROUP - International Contact: [name]
	Legal Representative (where applicable)	Not Applicable

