2.4 Endpoints

The primary endpoints will be:

- i. Overall binocular vision satisfaction after one week of wear;
- ii. Overall preference at the completion of the study.

The secondary endpoints will be:

- i. Mean binocular visual performance measured by timed logMAR mean visual acuity after one week of wear;
- ii. Number of contact lenses needed per participant to determine the contact lens pair to be dispensed.

[REDACTED]

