The participants medical, ocular, contact lens wearing history and concomitant treatments will once again be reviewed. [REDACTED] A series of measurements of visual acuity with the study contact lenses will be conducted for distance, intermediate and near as required. Contact lens fitting characteristics will be evaluated, and Order 1 contact lenses will be removed.

Upon removal of the Order 1 study contact lenses the other study contact lens (either test or control based upon the contact lens type used at Order 1) will be inserted and worn for 10 minutes at which time the contact lens fit and vision will be assessed and up to three attempts will be made to determine the optimal correction following the same protocol as during visit 1. If this is not achieved the participant will be discharged from the study, however, if a suitable fit is achieved the participants will be instructed in their use and care and the

contact lenses which will be dispensed. The participants will be instructed to wear the study contact lenses for at least 8 hours a day, at least 6 days a week and scheduled for their next study visit in 7 to 9 days.

Visit 3 – Contact Lens Order 2 Follow-up / Discharge Visit

Participants will return for their last follow-up visit having worn the last study lenses for 7 +2 / -0 days. They will attend the visit wearing the study contact lenses,

The participants medical, ocular, contact lens wearing history and concomitant treatments will once again be reviewed. [REDACTED] A series of measurements of visual acuity with the study contact lenses will be conducted for distance, intermediate and near as required. Contact lens fitting characteristics will be evaluated, and Order 2 study contact lenses will be removed. Upon contact lens removal and safety evaluation the participants will be discharged from the study.

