6.4 Procedures

6.4.1 Endpoint Procedures

The primary efficacy procedures will be:

- i. Rating overall vision satisfaction on a 100-point Visual Analog Scale (VAS) at the completion of one week of wear [REDACTED]
- ii. Rating overall preference on a 5-point scale at the completion of the study [REDACTED]

The secondary efficacy procedures will be:

- i. Measurement of mean binocular visual performance by the calculation of the mean visual acuity measured using timed logMAR charts after one week of wear under the following conditions:
 - Distance (at 4 meters) at high luminance (250cd/m²) with high (90%) contrast chart and low luminance (2.5cd/m²) with high (90%) contrast chart
 - Intermediate (at 67cm) at medium luminance (50 cd/m²) with high (90%) contrast chart
 - Near (at 40cm) at medium luminance (50 cd/m²) with high (90%) contrast chart
- ii. Recording of the number of contact lenses needed per eye to determine the contact lens to be dispensed;

[REDACTED]

- i. [REDACTED]
- ii. [REDACTED]
- iii. [REDACTED]
- iv. [REDACTED]
- v. [REDACTED]
- vi. [REDACTED]
- vii. [REDACTED]
- viii. [REDACTED]
- ix. [REDACTED]
- x. [REDACTED]
- xi. [REDACTED]
- xii. [REDACTED]
- xiii. [REDACTED]
- xiv. [REDACTED]
- xv. [REDACTED]
- xvi. [REDACTED]
- xvii. [REDACTED]
- xviii. [REDACTED]
- xix. [REDACTED]
- xx. [REDACTED]

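### The Visit 3 routine names only distance and near for timed logMAR acuity, but the secondary endpoint is a mean that also includes intermediate acuity at 67 cm

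*Combined protocol and SAP*

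**What the plan says.** Section 2.4 gives the first secondary endpoint as "Mean binocular visual performance measured by timed logMAR mean visual acuity after one week of wear". Section 6.4.1 says how it is obtained: "Measurement of mean binocular visual performance by the calculation of the mean visual acuity measured using timed logMAR charts after one week of wear". It then lists the conditions. Distance at 4 m is tested at 250 and at 2.5 cd/m², near is tested at 40 cm, and between them stands "Intermediate (at 67cm) at medium luminance". All use the high contrast chart.

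Section 6.5 sets out the visit-by-visit routine that staff are to follow. Its timed logMAR line for Visit 2 is "Detailed timed logMAR visual acuity without over refraction (monocular & binocular", with no viewing distance named. The line for Visit 3 is "Detailed timed logMAR visual acuity distance and near without over refraction (monocular & binocular".

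The narrative in section 6.2 uses one sentence for both visits: "A series of measurements of visual acuity with the study contact lenses will be conducted for distance, intermediate and near as required". It does not name the timed logMAR charts.

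The synopsis labels Visit 3 "Second lens follow up visit/Exit". Section 6.2 closes that visit with "Upon contact lens removal and safety evaluation the participants will be discharged from the study".

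**The concern.** The Visit 2 line is compatible with section 6.4.1; the Visit 3 line is not. Section 12.1 says the eCRFs are designed around each visit's testing routine, so a form built from the Visit 3 line could lack a field for intermediate acuity.

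In this crossover each participant wears the second lens for one week and is assessed with it once, at Visit 3. If intermediate acuity is not measured then, it exists for one lens per participant at most. The comparison at 67 cm would be lost, and so would the within-participant difference in the four-condition mean. Because participants leave the study at that visit, neither could be recovered.

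This mean is the visible endpoint for the secondary non-inferiority hypothesis on binocular visual performance in section 2.3. The two primary endpoints, vision satisfaction and preference, do not depend on it.

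**Working it through.** **Count of conditions**

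| Condition | 6.4.1 | 6.5 Visit 2 line | 6.5 Visit 3 line |
|---|---|---|---|
| Distance, 250 cd/m² | required | not restricted | covered |
| Distance, 2.5 cd/m² | required | not restricted | covered, if distance means both luminances |
| Intermediate, 67 cm | required | not restricted | not named |
| Near, 40 cm | required | not restricted | covered |

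Section 6.4.1 needs four; the Visit 3 line gives at most three.

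**Inputs for the size of the effect.** Everything below applies only if Visit 3 omits intermediate. The documents give no acuity values, so the gaps are assumptions, as is 0.02 logMAR per letter. Section 6.4.1 states no weights; I take the mean as equal weight on the four measurements, which is the natural reading.

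**Change of composite.** Weights on distance, intermediate and near:

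- four conditions: 2/4, 1/4, 1/4
- three conditions: 2/3, 0, 1/3

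**Case A: both lenses compared on the three remaining conditions.** Let m3 be the average lens effect over those three and dI the lens effect at 67 cm.

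- Four-condition difference: D4 = (3 × m3 + dI)/4
- Three-condition difference: D3 = m3
- D3 − D4 = (m3 − dI)/4

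| Assumed gap between m3 and dI (logMAR) | Change in lens difference (logMAR) | Letters |
|---|---|---|
| 0 | 0 | 0 |
| 0.05 | 0.05/4 = 0.0125 | 0.0125/0.02 = 0.625 |
| 0.10 | 0.10/4 = 0.025 | 0.025/0.02 = 1.25 |

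**Case B: four conditions at Visit 2, three at Visit 3.** Let g be the gap between intermediate acuity and the mean of the other three. Each Visit 3 mean shifts by s = g/4. The shift enters the test-minus-control difference with opposite sign in the two orders, so without period adjustment the average bias is s × (n1 − n2)/(n1 + n2). With the planned 25 completers and an assumed 13:12 split this is s/25.

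| Assumed g (logMAR) | Shift s = g/4 | Bias at 13:12 = s/25 | Letters |
|---|---|---|---|
| 0.05 | 0.0125 | 0.0005 | 0.025 |
| 0.10 | 0.025 | 0.001 | 0.05 |
| 0.20 | 0.05 | 0.002 | 0.1 |

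The mismatch therefore acts mainly as a period effect. It biases the lens comparison very little when the orders are near balanced, and not at all if period is modelled. Without a period term, each participant's difference still carries plus or minus s according to order, which adds noise.

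**The case against.** The strongest reply is that the protocol, read as a whole, already calls for intermediate acuity at Visit 3. Section 6.4.1 makes no exception by visit. Section 6.2 mentions intermediate under Visit 3, and the only visible requirement for it is the timed logMAR list. The Visit 3 line does not say that distance and near are the only tests. It also gives no luminance or contrast, so staff must turn to section 6.4.1 to run the test and would find intermediate there. The Snellen line just above contains the same distance-and-near wording, which suggests a copying slip. Several Visit 3 items, some footnotes and part of section 7.2 are redacted, so an intermediate measurement elsewhere cannot be excluded.

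Much of this stands. A slip is the likely explanation, and actual data loss is a risk rather than a certainty. It does not remove the conflict. The section 6.2 sentence leaves the measurement to be done as needed and does not name the chart. The Visit 3 timed logMAR line is complete and unredacted, and it disagrees with section 6.4.1 whatever the hidden items contain.

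Two further points are fair:

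- **Weights.** A mean over three viewing distances at 1/3 each is a possible reading. The divisor would then be 3 rather than 4, with the gap taken against the average of distance and near: gaps of 0.05 and 0.10 would give about 0.017 and 0.033 logMAR.
- **Order balance.** Section 6.3.1 states no blocking, so 13:12 is not guaranteed. At 15:10 the case B bias would be s × 5/25, or 0.0025 to 0.01 logMAR for the same gaps.

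Neither changes the finding or the remedy.

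**Conclusion.** The concern holds. The Visit 3 line in section 6.5 contradicts the endpoint definition in section 6.4.1 and should be corrected. I am confident of the textual conflict, and less so that data would in fact be lost, given the redactions and the likely slip.

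If the line is followed literally, the four-condition lens difference can be computed for none of the planned 25 completers. The three-condition fall-back is a different estimate, by an amount that could be nil or, on the case A assumptions, up to 0.025 logMAR. The visible text gives no logMAR margin to set this against, so I cannot say whether it would alter the non-inferiority conclusion. The bias from mixing composites is negligible if the orders are nearly balanced. The damage is confined to one secondary endpoint, and no figure stated in the plan changes.

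**What to change.** In section 6.5, rewrite the Visit 3 timed logMAR line to list the four conditions of section 6.4.1, or to refer to that list explicitly. Put the same wording in the Visit 2 line; that line conflicts with nothing, but matching text prevents the two visits from diverging. Then check that the eCRFs for both visits have fields for all four binocular measurements.

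The cost is two lines of text and a form check. No procedure is added beyond what section 6.4.1 already requires. The change has to be in place before participants reach Visit 3, because the measurement cannot be made after exit.

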7 SAMPLE SIZE DETERMINATION AND STATISTICAL ANALYSIS

7.1 Sample Size Determination

[REDACTED]

[REDACTED]

[REDACTED] Based upon this data sample size estimation has been performed to demonstrate non-inferiority for the test Biofinity® multifocal fitting compared with the control Biofinity® multifocal fitting postulating a true difference of 20% and a margin of equivalence 10%. Calculation based upon a one-sided binomial test with $\alpha = 0.025$, $\beta = 0.200$ gives a minimal samples size of 23 participants.

Based upon the above up to 30 participants will be screened with a view to achieve a per protocol population (PPP) of 25 participants.

Participants will be considered enrolled when they successfully complete the screening visit.

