2 INTRODUCTION AND RATIONALE

2.1 Background

Biofinity® Multifocal CE marked contact lenses are the basis of a well established eight-design multifocal system to correct presbyopia. As for any multifocal contact lenses the performance and acceptance of the vision correction depends in part upon the patient’s ocular characteristics leading practitioners to follow different fitting approaches to achieve the best results. [REDACTED]

[REDACTED]

The rationale for the study is to compare two common fitting approaches to fit Biofinity® Multifocal contact lenses to assess which one achieves the best results to support proposing that fitting approach for the selection of the first contact lenses to try.

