2.3 Hypotheses

The primary hypotheses to be tested will be that:

- i. Overall vision satisfaction with Biofinity® Multifocal (Biof MF) contact lens after one week of wear is non-inferior for the test contact lens [REDACTED]
- ii. Overall preference between Biofinity® Multifocal (Biof MF) contact lens is non-inferior for the test contact lens [REDACTED]

The secondary hypotheses to be tested will be that:

- i. Overall binocular visual performance with Biofinity® Multifocal (Biof MF) contact lens after one week of wear is non-inferior for the test contact lens [REDACTED]

[REDACTED]

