5.2 Number of Participants

Up to 30 participants will be screened, with the aim to enrol up to 27 with a view to achieve a cohort (participants completing the study as per protocol) sample size of 25 which has been determined to be optimal, balancing the need for sufficient discrimination and limiting inconvenience to participants by not inflating the study sample (see section 7.1).

Up to 30 participants will be screened with a view to achieving a per protocol population of 25 participants. Participants will be considered enrolled when they successfully complete the screening visit.

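### Section 2.1 asks which fitting is best, but the readable hypotheses and sizing test only non-inferiority of the test fitting; a pre-specified superiority step would close the gap at the same 25 participants

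*Combined protocol and SAP*

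**What the plan says.** Section 2.1 (Background) ends with a complete, unredacted sentence giving the rationale: two common ways of fitting the same multifocal lens are compared "to assess which one achieves the best results to support proposing that fitting approach" for the first lenses tried.

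The objectives in section 2.2 are neutral; they speak of comparing satisfaction and preference.

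Section 2.3 (Hypotheses) turns to non-inferiority. On vision satisfaction, the lens "after one week of wear is non-inferior for the test contact lens". On preference: "Overall preference between Biofinity® Multifocal (Biof MF) contact lens is non-inferior for the test contact lens". The visible secondary hypothesis takes the same form.

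Section 7.1 says "sample size estimation has been performed to demonstrate non-inferiority for the test" fitting against the control, "postulating a true difference of 20% and a margin of equivalence 10" per cent, with a one-sided binomial test, alpha 0.025 and beta 0.200. This "gives a minimal samples size of 23 participants", and the plan aims for 25 per protocol. Section 5.2 describes a "sample size of 25 which has been determined to be optimal, balancing the need for sufficient discrimination" against inconvenience to participants.

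Under section 6.4.1, the two primary endpoints are a 100-point visual analog scale (VAS) for satisfaction and a 5-point preference scale. Parts of sections 2.2, 2.3, 7.1 and 7.2 are redacted. Section 7.2 leaves the detailed analysis plan to be written before database closure.

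**The concern.** Which of two fittings is best, and whether one is no worse than the other by more than a margin, are different questions. Meeting non-inferiority rules out a deficit larger than the margin; it does not show an advantage. Missing it does not show that the control is better. No readable text links the non-inferiority result to the choice that section 2.1 wants the study to support.

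At stake is the recommendation of a first-try fitting. Unless the rule for claiming an advantage is fixed in advance, a non-inferiority result could come to carry more weight than it bears. The 80% in section 7.1 could also be taken as the chance of identifying the better fitting, when it is the chance of meeting the weaker criterion.

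**Working it through.** **Inputs from section 7.1.** Difference 20 points, margin 10 points, one-sided alpha 0.025, power 80%, binomial test, minimum 23, planned 25.

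**Assumptions.**
- The outcome has two categories and is analysed as one sample against a reference proportion *b*.
- The 20 points favour the test fitting. The direction is not stated, but a 20-point deficit would exceed the 10-point margin.
- *b* is not visible, so it is varied.

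**Method.** For a null proportion p0, the critical count r is the smallest count with P(X ≥ r | n, p0) ≤ 0.025. Power is P(X ≥ r | n, p1), with p1 = *b* + 0.20. For non-inferiority p0 = *b* − 0.10; for superiority p0 = *b*.

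**Step 1: reproduce the 23.** Exact power rises and dips as n grows. The second column therefore gives the first n reaching 80% and the n from which power stays there.

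| Reference *b* | n for 80%, non-inferiority (first / stays) | Critical count, non-inferiority, n = 25 | Power, non-inferiority | Critical count, superiority, n = 25 | Power, superiority |
|---|---|---|---|---|---|
| 0.35 | 21 / 23 | 12 | 81.7% | 15 | 38.4% |
| 0.40 | 23 / 25 | 13 | 84.6% | 16 | 42.5% |
| 0.45 | 24 / 26 | 15 | 77.1% | 17 | 46.7% |
| 0.50 | 22 / 24 | 16 | 81.1% | 18 | 51.2% |
| 0.55 | 22 / 25 | 17 | 85.1% | 20 | 37.8% |
| 0.60 | 20 / 23 | 18 | 89.1% | 21 | 42.1% |
| 0.65 | 20 / 23 | 20 | 83.8% | 22 | 47.1% |

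The 23 lies within the first/stays range at every reference from 0.35 to 0.65 except 0.45, where it is one below. It is the first n exactly at 0.40. So the model is consistent with section 7.1, and 25 participants deliver roughly the stated 80% for non-inferiority (77-89%).

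At *b* = 0.70 the answer is 19 on both counts, which does not give 23, so that case is left out. At *b* = 0.30 the range is 19 / 24 and superiority power is 50.0%, inside the range below.

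**Step 2: superiority at the same n and the same 20 points.** Power runs from 37.8% to 51.2%. Subtracting row by row, non-inferiority would be met without superiority being shown in 30% of trials (81.1 − 51.2 = 29.9 at 0.50) to 47% (85.1 − 37.8 = 47.3 at 0.55).

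**Step 3: an example at *b* = 0.50.** Non-inferiority needs 16 of 25 and superiority needs 18. The exact 95% intervals are 42.5-82.0% for 16 of 25, 46.5-85.1% for 17 and 50.6-87.9% for 18. With 16 or 17 the test fitting is non-inferior, but the interval still includes 50%.

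**Step 4: dependence on the model.** With the same 20 points, n = 25 and references of 0.35 to 0.65, the normal approximation gives 52-57% and the arcsine approximation 52-65%. A paired exact McNemar test gives 12-38%, depending on the share of discordant pairs. All are below 80%.

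For the VAS, power depends on the within-person standard deviation (SD), which is not visible. If a paired t-test were used at one-sided 0.025 with n = 25, power would be 48%, 67% and 82% at assumed standardised differences of 0.4, 0.5 and 0.6. No single figure covers both primary endpoints.

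**The case against.** The statistical chain agrees with itself: neutral objectives, non-inferiority hypotheses, non-inferiority sizing. The outlier is one sentence of background, labelled a rationale and not a decision rule. Best could also be meant more broadly. The number of lenses needed is a secondary endpoint (section 2.4), and a fitting with non-inferior satisfaction that needs fewer trial lenses might reasonably be proposed first. This lowers the weight of the point. It does not remove it, because section 2.1 says what choice the result is to support and no readable text says how a non-inferiority result would settle it.

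Four stronger readings are tempting, and the documents do not support them.

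- *The study is too small.* Its stated target is 80% for non-inferiority, and that is delivered. Lower power for a different claim is not an error in the sizing.
- *There is no superiority step.* One may sit in redacted text or in the detailed analysis plan still to come.
- *Power to show an advantage is 38-51% for the trial.* That holds only for the two-outcome model above. It does not carry over to the VAS or to a 5-point scale that is not dichotomised.
- *Non-inferiority will be reported as best, or a miss as a win for the control.* No passage plans either.

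**Conclusion.** The mismatch is real and stands in readable text: section 2.1 asks a which-is-better question, while sections 2.3 and 7.1 state and size only non-inferiority of the test fitting. Neither outcome of that test can by itself show that one fitting is better.

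The size is about 38-51% power to show the test fitting better with 25 participants, against the 80% stated for non-inferiority. It rests on the two-outcome, one-sample exact binomial reading, a 20-point advantage for the test fitting and a reference proportion of 35-65%. Superiority power on the VAS remains unknown.

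The point is minor. It asks for a pre-specified step and a clear statement of what the 80% covers, and it leaves the sample size alone.

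**What to change.** Keep 25 participants. In the detailed analysis plan, where redacted text does not already do so:

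1. For each primary endpoint, pre-specify a superiority test at one-sided 0.025, carried out only if non-inferiority is met on that endpoint. Tested in this order, it costs no alpha within the endpoint.
2. Report the two-sided 95% interval for each endpoint, so that evidence in either direction can be seen.
3. Claim best or better only if superiority is shown.
4. State in section 7.1 that the 80% applies to non-inferiority. Give superiority power separately for each primary endpoint, from the sponsor's own reference proportion and the SD of the within-person VAS difference, and not as one figure for the trial.

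The cost is one extra pre-specified test per primary endpoint and an openly stated lower power for showing an advantage. No visits or participants are added.
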